13.3 Sample Size Determination

13.3.1 Incidence of IOP ≥ 30 mmHg

Due to their comparable rheological properties, DVisc40 and VISCOAT® OVDs are expected to demonstrate similar behavior during surgical procedures.

In published studies using VISCOAT®, VISCOAT® performed without anti-IOP prophylactic treatment where the frequency of IOP spikes ≥ 30 mmHg after surgery ranged from 0.0% to 47.5%.⁶⁻²³ Based on these studies the control OVD incidence of subjects who experience at least one IOP observation ≥ 30 mmHg is estimated to be 0.117 (11.7%). A doubling of the control OVD incidence would be problematic and clinically significant, thus the non-inferiority margin will be defined as equal to the expected rate of 0.117 (11.7%).

When the sample size in each group is 165 subjects, a two-group large-sample normal approximation test of proportions with a one-sided 0.050 significance level will have 95.17% power to reject the null hypothesis that the test is inferior to the control (the difference in proportions, $\pi_t - \pi_c$, is 0.117 or greater) in favor of the alternative hypothesis that the test is non-inferior to the control (the difference in proportions, $\pi_t - \pi_c$, is less than 0.117), assuming that the expected difference in proportions is 0.000 and the proportion in the standard group is 0.117.

13.3.2 ECD Loss

The standard deviation of the ECD loss percentage with VISCOAT® is estimated to be 14.2%.²⁴ When the sample size in each group is 165 subjects, a two group 0.050 one-sided t-test will have 93.90% power to reject the null hypothesis that the test is inferior to the control (the difference in means, $\mu_t - \mu_c$, is 5% or greater) in favor of the alternative hypothesis that the test is non-inferior to the control (the difference in means, $\mu_t - \mu_c$, is less than 5%), assuming that the expected difference in means is 0% and the common standard deviation is 14.2%.

13.3.3 Overall Power and Adjustment for Dropouts

Assuming independence of the primary endpoints, the overall power of the study will be $95.17\% \times 93.90\% = 89.36\%$.

To allow for a dropout rate of up to 10%, a sample size of approximately $[165/(1 - 0.1)] = 184$ subjects per arm will be targeted for enrollment. The total enrollment target therefore will be approximately 368 subjects.

13.3.4 Detectable Effect Sizes for the Secondary Hypothesis Tests

The secondary effectiveness hypothesis will be tested only if both primary endpoint statistical tests are successful. If the primary endpoints are met and the secondary effectiveness hypothesis is met, then the type I error rate for the three secondary safety hypothesis tests will be controlled using the Holm stepwise procedure. Under this procedure, the smallest of the three raw p-values will be compared to 0.025/3 or, equivalently, tripled

and compared to 0.025. Consequently, detectable effect sizes for one-sided tests with 80% power are presented based on an alpha risk of 0.008.

13.3.4.1 Secondary Safety Hypothesis Tests

13.3.4.1.1 Incidence of $IOP \geq 30 \text{ mmHg}$

A two-group χ^2 test with a 0.008 one-sided significance level will have 80% power to detect the difference between a test group proportion, π_1 , of 0.117 and a control group proportion, π_2 , of 0.256 when the sample size in each group is 165.

13.3.4.1.2 Mean Change from Baseline in IOP

A sample size of 165 in each group will have 80% power to detect a difference in means of 1.797 mm Hg assuming that the common standard deviation is 5.0 mm Hg using a two-group t-test with a 0.008 one-sided significance level.

13.3.4.2 Secondary Effectiveness Hypothesis Test: ECD Loss

A sample size of 165 in each group will have 80% power to detect a difference in means of 4.393 % assuming that the common standard deviation is 14.2 % using a two-group t-test with a 0.025 one-sided significance level.

13.4 Analysis Populations

13.4.1 Intent-to-Treat Population

The Intent-to-treat (ITT) Population will include all eyes that were randomized.

13.4.2 Safety Population

The Safety Population will include all eyes that were exposed to either the test OVD or the comparator OVD. Study eyes that discontinue prior to OVD exposure will be excluded from the Safety Population.

13.4.3 Per Protocol Population

The Per Protocol (PP) Population will include all randomized eyes without major protocol deviations. Protocol deviations resulting in exclusion from the PP Set are described in Section 13.5.7.

13.4.4 Best Case Population

The Best Case Population will include all Per Protocol eyes without intraoperative complications. Intraoperative complications, as documented in the Day 0 Surgeon Questionnaire (*cf.* [Appendix C](#)), will be reviewed in a masked fashion by the Sponsor prior to database lock to determine which PP population cases warrant exclusion from the Best Case Population.

13.5 Statistical Analysis

Summaries for continuous variables will include the sample size, mean, standard deviation, median, minimum, and maximum. Summaries for categorical variables will include the tabulation of frequencies and percentages.

13.5.1 Primary Safety Analysis

IOP will be assessed in the study eye using Goldmann tonometry at each scheduled follow-up visit and may be assessed at unscheduled visits.

Subjects with $IOP \geq 30$ mmHg at any follow-up visit ($IOP \geq 30$ mmHg at any follow-up visit, No $IOP \geq 30$ mmHg at any follow-up visit) will be summarized using categorical summary statistics for the Safety Population by actual treatment received in a table. Missing data will not be imputed for this summary table.

Missing IOP values will be imputed using Markov chain Monte Carlo (MCMC) methods. Twenty imputed datasets will be produced using a seed of 1017144149. The variables used in the imputation model will include IOP at baseline and at each of the scheduled postoperative visits. After missing data at scheduled visits has been imputed, unscheduled visit IOP values will be added to each imputed dataset.

Within each imputed dataset, subjects will be classified as belonging to one of the following groups:

- $IOP \geq 30$ mmHg at any follow-up visit
- No $IOP \geq 30$ mmHg at any follow-up visit

This classification will be based on experiencing at least one IOP measurement of 30 mmHg or more at any follow up visit over the entire course of the study. Subjects experiencing one or more IOP spikes will be counted only once.

The difference between test and control in the proportion of subjects with $IOP \geq 30$ mmHg at any follow-up visit and the asymptotic standard error will be estimated separately for each imputation.

An estimated difference between treatment groups and a two-sided asymptotic Wald 95% confidence interval around the difference will be constructed via combination of the proportion differences and standard errors from the imputations. If all the imputations result in the same estimated difference and confidence interval, then the results of a single imputation may be used.

If the upper confidence limit (equivalent to a one-sided upper 95% confidence limit) is less than 0.117 (11.7%), then the null hypothesis of inferiority will be rejected in favor of the alternative hypothesis of non-inferiority. A p-value will also be provided for this one-sided hypothesis test.

The primary safety analysis will be repeated using the Per Protocol Population as a sensitivity analysis with observed data only (i.e. without imputation).

In addition to the primary analysis, sensitivity analyses will include a best-case analysis, a worst-case analysis, and a complete case analysis (which will include only data from subjects who have IOP measurements at every scheduled follow-up visit).

Poolability of results across centers will be assessed by performing a Cochran-Mantel-Haenszel test comparing the endpoint between the treatment groups stratified by center. The p-value for the Breslow-Day test for homogeneity of odds ratios across centers will be compared to a critical value of 0.15.

The previous analyses will be completed for the following two groups, separately, without the sensitivity analyses and poolability test:

- Subjects who received IOP-reducing intervention; and
- Subjects who did not receive IOP-reducing intervention.

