9.1.3 Treatment Replacement

No other OVD can be used intraoperatively in conjunction with either the test or control OVD. Use of any other OVD will require immediate discontinuation of a subject from the study. If the surgeon feels more than one vial of test or control OVD is required to complete the surgery, this will be allowed and the incidence of such events will be reported.

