13.5.2 Primary Effectiveness Analysis

Specular microscopy of the central cornea will be completed preoperatively and at Visit 5 (90 ± 14 days postop). Images will be evaluated by a masked reading center. If multiple cell densities are obtained from the reading center for each eye visit, then the available counts will be averaged by eye and visit (Preoperative, Visit 5) to produce a single value for each eye visit.

If one or more ITT Population eyes has a missing mean ECD value either at the preoperative visit or at Visit 5 (including due to a missed visit or due to discontinuation), then the missing data will be imputed as follows. Prior to analysis, 25 imputations of missing mean densities will be produced using the Markov chain Monte Carlo method and the variables investigator, treatment, preoperative value, and postoperative value.

For each observation in the imputed datasets, the ECD loss in percent at Visit 5 will be calculated for each eye at each visit as follows:

$$\text{Loss (\%)} = \frac{\text{Preoperative Cell Density} - \text{Visit 5 Cell Density}}{\text{Preoperative Cell Density}} \times 100\%$$

The means and standard errors from the imputed datasets will be combined to produce a continuous variable summary of the ECD (cells / mm^2) at each visit (Preoperative, Visit 5) and the percent loss at Visit 5 by randomized treatment assignment for the ITT Population.

Loss (%) will be modeled as a function of the fixed class variables treatment and investigator, separately by imputation. The parameter estimates will be combined to produce a one-sided upper 95% confidence limit for the difference in percent loss between the test

and comparator OVDs and a p-value for the hypothesis test for the ITT Population. If the upper confidence limit is less than 5%, then the null hypothesis of inferiority will be rejected in favor of the alternative hypothesis of non-inferiority.

If there are no ITT Population eyes with missing ECD data, then imputation will not be performed. Instead, the available data will be analyzed and summarized as described above.

Sensitivity analyses of effectiveness will include a best-case analysis, a worst-case analysis, a tipping point analysis, and a complete case analysis (which will use only subjects who have cell density measurements at every scheduled visit), and analysis using the PP Set.

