13.5.7 Protocol Deviations

The number of subjects within each type of protocol deviation will be presented using discrete summary statistics.

Major protocol deviations leading to exclusion from the PP Set will include the following.

- Ineligibility
- Use of an incorrect OVD including misrandomized subjects
- Disallowed concomitant treatments including IOP lowering treatments
- Missing IOP value at postoperative visit 1 or 2

Additional major protocol deviations may be identified prior to unmasking of the treatment assignments.

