13.7.3 Multiplicity Issues

Statistical success will require demonstration of non-inferiority in both the primary safety and effectiveness endpoints for the primary analysis populations. Therefore, no adjustments for multiplicity are required for the primary hypothesis tests. The first secondary hypothesis test will be eligible for evaluation only if the primary endpoints are met. Therefore, no adjustment for multiplicity will be necessary. The secondary hypothesis tests in the last family of hypotheses will be adjusted for multiplicity using the Holm stepwise procedure.

14 Quality Control and Quality Assurance

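### The imputation model for the primary IOP safety test leaves out treatment, which shrinks a true arm difference modestly toward non-inferiority

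*Combined protocol and SAP*

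**What the plan says.** Section 13.5.1 sets out the imputation behind the primary safety comparison: "Twenty imputed datasets will be produced using a seed of 1017144149". On the model it says: "The variables used in the imputation model will include IOP at baseline and at each of the scheduled postoperative visits". Unscheduled IOP readings are added after imputation, each eye is classed as having a reading of 30 mmHg or more or not, and the arm difference is combined over the imputations and compared with 0.117.

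For the other primary endpoint, Section 13.5.2 imputes ECD with "the Markov chain Monte Carlo method and the variables investigator, treatment, preoperative value, and postoperative value". Treatment is therefore specified for one primary endpoint and not for the other, and no reason is given.

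Two provisions make missing early IOP foreseeable. Section 13.5.7 counts "Missing IOP value at postoperative visit 1 or 2" among the major deviations. Section 9.1.3 states: "Use of any other OVD will require immediate discontinuation of a subject from the study"; this can leave an exposed eye without scheduled postoperative readings.

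Section 13.7.3 ties the trial's outcome to the primary analyses: "Statistical success will require demonstration of non-inferiority in both the primary safety and effectiveness endpoints for the primary analysis populations".

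**The concern.** A model that fills in values for a between-arm comparison should contain the arm. If it does not, a missing reading in either arm is drawn from a distribution averaged over both OVDs, except for what the eye's other readings reveal about its arm. Imputed eyes then look more alike across arms than they are, and the estimated difference moves toward zero.

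In a superiority test that would be conservative. In a non-inferiority test it favours success when the test product is worse. The endpoint is sensitive to this because one early reading can decide whether an eye counts as a spike. At stake is the false-positive rate of one of the two tests on which the trial's success rests.

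**Working it through.** **Inputs from the plan.** Control spike rate 0.117, margin 0.117, one-sided 0.05, 165 evaluable per arm (13.3.1); 184 enrolled per arm after a 10% dropout allowance (13.3.3); 20 imputations (13.5.1). At the margin the test rate is 0.117 + 0.117 = 0.234.

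**Reproducing the plan's power.** SE = sqrt(2 × 0.117 × 0.883 / 165) = 0.0354. Power = Φ(0.117/0.0354 − 1.645) = Φ(1.66) = 95.17%, as stated in 13.3.1.

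**Largest possible shrinkage.** If a share m of eyes in each arm has its spike status filled from a fully pooled model, the expected difference is (1 − m) × (π_t − π_c). At m = 0.10 this is 0.90 × 0.117 = 0.1053, or 10.5 points instead of 11.7. The chance of falsely concluding non-inferiority is then Φ((0.117 − 0.1053)/SE − 1.645). The imputed rates are 0.9 × 0.234 + 0.1 × 0.1755 = 0.2282 and 0.9 × 0.117 + 0.1 × 0.1755 = 0.1229. With 184 per arm, SE = 0.0393, which gives Φ(−1.35) = 8.9%. The same formula gives 6.7% at m = 0.05 and 5.65% at m = 0.02. These are upper figures: they ignore the between-imputation variance and any arm information carried by the eye's other readings.

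**Simulation with multiple-imputation variance.** There were 20,000 runs per IOP shape at the margin, with 184 per arm, 20 multivariate-normal imputations, Rubin's rules and Wald variance. The following are assumptions, not from the plan: two IOP shapes (normal and right-skewed); 93-97% of control spikes at 6 hours; values missing completely at random and equally in both arms; either the 6-hour reading alone or all postoperative readings missing. Ranges span shapes and patterns.

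| Early IOP missing | Eyes of 368 | False non-inferiority, treatment omitted | Treatment included | Paired excess (points) |
|---|---|---|---|---|
| 2% | about 7 | 5.1-5.5% | 4.7-5.0% | 0.2-0.5 |
| 5% | about 18 | 5.3-6.0% | 4.5-4.7% | 0.7-1.3 |
| 10% | about 37 | 5.5-7.0% | 4.1-4.4% | 1.5-2.6 |

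Complete data in the same runs gave 4.9-5.1%. Monte Carlo error is about 0.15-0.18 points for the rates and 0.04-0.11 for the paired excess. At 10% missing, the mean estimated difference is 10.5-11.0 points without treatment and 11.7-11.8 with it.

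**Other simulations under different assumed IOP distributions.** At 10% missing, 5,000 runs per scenario gave 10.5-10.8 points without treatment against 11.6 with it, and false non-inferiority of 6.1-7.2% against 4.1-4.6% (complete data 5.2%). A smaller set of 1,400 runs gave 10.5 against 11.6 points, and about 8.0% against 5.1%. In 600-run sets at 2% and 5% missing, the inflation was within simulation error.

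**At a true difference of zero** (6,000 runs): no bias, and power of 96.8-97.1% without treatment against 96.2-96.8% with it.

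**If the two-sided limit is used.** Section 13.5.1 says "An estimated difference between treatment groups and a two-sided asymptotic Wald 95% confidence interval around the difference will be constructed" and then treats its upper limit as a one-sided 95% limit. The upper end of a two-sided 95% interval has nominal one-sided error of 2.5%. On that reading the rates are 2.7-3.5% against 1.9-2.1% at 10% missing. At 2% missing they are 2.5-2.8% against 2.3-2.6%, which is close to noise.

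**The case against.** **The list may not be complete.** The variables are said to include IOP values, which is not exclusive wording, and Section 13 defers further detail to a SAP approved before database lock. Treatment may yet be added. But nothing in the supplied text adds it, a seed and number of imputations are already fixed, and the ECD list names treatment explicitly. Followed as written, the rule is biased when the arms differ.

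**The effect is small.** This largely stands. Visit 1 takes place on the day of surgery; out-of-window readings still go on the scheduled-visit form (11.1.4); unscheduled readings are added back (13.5.1); and 8.3.4 asks for every effort to obtain data before discontinuation. The 10% in 13.3.3 is whole-study dropout, so it is only an upper scenario for early visits. The paired excess also uses a comparator that runs below the nominal 5%. Subtracting range endpoints against complete data, the excess is about 0-0.6 points at 2% missing, 0.2-1.1 at 5% and 0.4-2.1 at 10%.

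**Other analyses would reveal it.** The Per Protocol observed-data, best-case, worst-case and complete-case analyses do not use the pooled fill and could expose a dependent result. They are sensitivity analyses, however, and success rests on the primary analysis. The tipping-point analysis listed for ECD is not listed for IOP.

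**The choice of confidence limit matters more.** Moving between 5% and 2.5% nominal error outweighs this omission. That is a separate inconsistency; the direction of the bias and the remedy are the same under either reading.

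**Conclusion.** The point holds and should be fixed. As specified, the IOP imputation does not condition on treatment, so a true disadvantage of the test OVD is understated in the primary safety test. The shrinkage is at most m times the true difference: 1.2 points at the margin with 10% missing, and about 0.2 points with 2% missing. In the main simulation, false non-inferiority at one-sided 0.05 reaches 5.5-7.0% at 10% missing and stays close to nominal at 2%. There is no bias if the arms are equal.

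The size rests on the assumed missingness rate, IOP distributions and missing-at-random pattern, none of which the plan provides. The direction depends only on the omission and on the arms truly differing.

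**What to change.** Before database lock, add treatment to the IOP imputation variables in Section 13.5.1, using the same treatment variable as the comparison, as Section 13.5.2 already does for ECD. Imputing separately within each arm is an alternative. Adding investigator, age group or cataract severity is optional. The wording on the two-sided interval and the one-sided limit should be reconciled in the same edit.

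The cost is one line of SAP text and one line of code, with no change to data collection. At 10% missing the mean standard error is 4.1 points with or without treatment in the model, and the loss of power at zero difference is well under one point on the ranges shown.

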9.1.2 Randomization Method

Subjects will be randomly assigned to one of the two OVD materials according to the randomization scheme to be provided in a computer-generated randomization code by a biostatistician otherwise not involved with the study.

Interactive Response Technology (IRT) will be utilized for randomization in this study. Randomization will be stratified by site, age group and cataract severity. A method other than stratification may be employed to balance randomization. If so, the method will be specified in the SAP. The randomization codes will be established in blocks such that approximately the same number of subjects will be assigned to the DVisc40 OVD or VISCOAT® OVD treatment groups at each site.

Subjects will be randomized to 1 of 2 treatment groups in a ratio of 1:1 (DVisc40:VISCOAT®). Each screened subject will be assigned a unique 5-digit subject number assigned by the site accessing the IRT system. The subject number assigned by the IRT system will consist of the 2-digit investigational center/site number (pre-assigned by Sponsor or its designee) and the 3-digit chronological screening order number starting with 001 (e.g. 01-001, 01-002). The study device kit will be assigned to subjects based on a randomization code and the kit will be dispensed to the subjects at Day 0 (Operative Visit) by the IRT system. The assigned kit number should be recorded in the subject's source documents and applicable case report form. A study device log will document the inventory and dispensing of study device at each investigational center.

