13.7.2 Multicenter Issues

Randomization will be stratified by site. Sites will be considered in the primary effectiveness analysis as described in Section 13.3 above. Poolability will be assessed as described in Section 13.3 above.

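### The primary safety interval leaves out site although randomization is blocked by site; if spike rates differ appreciably between sites, the test is mildly conservative

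*Combined protocol and SAP*

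**What the plan says.** **Allocation.** Section 9.1.2 states: "Randomization will be stratified by site, age group and cataract severity". It adds: "The randomization codes will be established in blocks such that approximately the same number of subjects will be assigned" to each arm at each site. It also leaves a way out: "A method other than stratification may be employed to balance randomization", in which case the SAP is to name the method. Appendix C has one surgeon operate at each site unless the sponsor approves an exception.

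**Primary safety analysis (13.5.1).** In each of 20 imputed datasets the difference in spike proportions is computed, and "the asymptotic standard error will be estimated separately for each imputation". Then a "two-sided asymptotic Wald 95% confidence interval around the difference will be constructed via combination of the proportion differences and standard errors". No site term or weight is stated. Site does not enter through the imputation either: "The variables used in the imputation model will include IOP at baseline and at each of the scheduled postoperative visits".

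**Where site is used.** In 13.5.1 it appears only in a poolability check, a "Cochran-Mantel-Haenszel test comparing the endpoint between the treatment groups stratified by center", with a Breslow-Day test. That check does not supply the limit compared with 0.117. The other co-primary analysis (13.5.2) fits treatment and investigator as fixed effects. Section 13.7.2 matches this split: "Sites will be considered in the primary effectiveness analysis as described in Section 13.3 above". The secondary spike-rate test (13.5.3.1.1) is a plain chi-square test.

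**The concern.** Blocking within site takes between-site differences out of the comparison of arms. A crude two-sample standard error still counts them as noise. If some sites have clearly higher spike rates than others, the interval is wider than the design warrants. Both co-primary endpoints must succeed (13.7.3), so avoidable width on either one is a cost. The plan also treats its two co-primary endpoints differently and gives no reason.

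**Working it through.** **Inputs from the protocol.** Control spike rate p = 0.117, margin 0.117, true difference 0, 165 eyes per arm, one-sided 0.05 (13.3.1). Up to about 18 sites (7.2), so about 368/18 = 20 eyes per site.

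**Assumed input.** The between-site SD of spike rates, τ. The documents do not give it, so a range is shown.

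**1. The plan's own figure.** With no site term, p(1 − p) = 0.117 × 0.883 = 0.10331. SE = √(2 × 0.10331/165) = 0.03539. Power = Φ(0.117/0.03539 − 1.645) = Φ(1.661) = 95.17%, which is the stated value.

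**2. Effect of blocking.** If site rates have mean p and SD τ, the average within-site variance is p(1 − p) − τ². With arms balanced in each site, the true SE of the difference is √(2[p(1 − p) − τ²]/165). The crude SE is therefore too large by the factor 1/√(1 − τ²/[p(1 − p)]).

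**3. Power.** Crude test: Φ((0.117 − z × 0.03539)/true SE). Stratified test: Φ(0.117/true SE − z). For τ = 0.10 and z = 1.645, the crude test gives (0.117 − 0.05821)/0.03363 = 1.748, or 96.0%. The stratified test gives 3.479 − 1.645 = 1.834, or 96.7%.

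| τ | True SE | Crude/true SE | Crude power | Stratified power | Gain, z = 1.645 | Gain, z = 1.960 |
|---|---|---|---|---|---|---|
| 0 | 0.03539 | 1.000 | 95.2% | 95.2% | 0 | 0 |
| 0.05 | 0.03496 | 1.012 | 95.4% | 95.6% | 0.2 | 0.4 |
| 0.08 | 0.03427 | 1.032 | 95.7% | 96.2% | 0.5 | 0.9 |
| 0.10 | 0.03363 | 1.052 | 96.0% | 96.7% | 0.7 | 1.4 |
| 0.14 | 0.03185 | 1.111 | 96.8% | 97.9% | 1.1 | 2.4 |

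The last column matters because 13.5.1 equates the upper limit of a two-sided 95% interval with a one-sided 95% limit. Programmed literally, it is a one-sided 97.5% limit, and base power is Φ(3.306 − 1.960) = 91.1%. That ambiguity is a separate point, and a larger one than the site term.

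**4. Simulation, 18 sites with 9 eyes per arm each, 40,000 runs.** Crude against actual SE was 0.0354/0.0346 = 1.02 at τ = 0.08, 0.0352/0.0335 = 1.05 at 0.11, and 0.0351/0.0321 = 1.09 at 0.14. Power gains at one-sided 0.05 were about 0.5, 0.9 and 1.4 points. The SE excess is a little below the closed form because each simulated trial draws only 18 site rates and the Wald formula uses estimated rates.

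**5. Simulation, 18 sites with 20 eyes each, 10,000 runs.**
- With no true difference, the SE ratio was 0.99, 1.02, 1.05 and 1.12 at τ = 0, 0.05, 0.10 and 0.15.
- Under simple randomization at τ = 0.10 it was 0.985, so the excess comes from the blocking.
- With four strata per site and blocks of 4 (both assumed) it fell to 1.03 at τ = 0.10 and 1.09 at 0.15.
- At a true difference of 0.117, the crude test's one-sided 5% error was 5.2%, 5.0%, 4.6% and 4.2% at the four values of τ. The Mantel-Haenszel test with Sato variance gave 5.1% to 5.6%.

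**The case against.** The strongest reply is that the unadjusted risk difference is a legitimate pre-specified contrast. It matches the sample-size formula, errs on the safe side, and keeps power at about the planned 95.17% in every scenario examined. All of that stands, and it keeps the point minor.

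Further limits also stand:
- A reader might infer that the SE is too large whenever site rates differ at all. It is not. In simulation the crude-to-actual ratio was 0.989 at an SD of 3 points and about 1.00 to 1.02 at 5 points.
- A reader might take the 0.0% to 47.5% range in 13.3.1 as evidence of wide site differences. That range is across published studies. It does not estimate the spread among sites working to one protocol, with common eligibility rules and no prophylactic IOP-lowering treatment.
- Balance within site is only approximate. Age group and cataract severity are also strata, so incomplete blocks shrink the excess. Another balancing method is allowed; the point survives only if that method still balances by site.
- The stratified test runs slightly above nominal size, so the change involves a small trade.

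The poolability check does not answer the point, because it leaves the decision interval unchanged. The SAP that section 13 announces could add a site adjustment, but the analysis as written has none.

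**Conclusion.** The point holds as a minor efficiency and consistency improvement. With blocking by site, the crude SE exceeds the true one by roughly 1% at a between-site SD of 5 points, 2-3% at 8, 5% at 10-11 and 9% at 14. The cost is about 0.3 to 1.4 power points at one-sided 0.05, and up to about 2.4 under a literal two-sided 95% limit. When sites do not differ there is no excess.

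This rests on an assumed between-site SD, near-equal arms within each site, and sites treated as fixed. Site stands for surgeon only under the one-surgeon rule in Appendix C.

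A reader might infer that the safety test is invalid or the trial underpowered. The documents support neither: false non-inferiority claims are not inflated, and crude power stays near plan. The chi-square test in 13.5.3.1.1 omits site in the same way, but its loss was not quantified.

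**What to change.** - **13.5.1:** keep the risk difference and the 0.117 margin. In each imputed dataset, estimate the Mantel-Haenszel site-stratified risk difference with its stratified SE (for example Sato), and combine as planned. Report the crude difference as a sensitivity analysis.
- **13.5.3.1.1:** replace the chi-square test with the site-stratified Cochran-Mantel-Haenszel test.
- **13.7.2:** state that site is used for both primary endpoints. Correct its cross-reference at the same time: it points to 13.3 (sample size), while the analyses are in 13.5.

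**Cost.** Some wording and a few lines of code, with no new data. Sites are sparse, at about 20 eyes and 20 × 0.117 = 2.3 expected spikes each, so Mantel-Haenszel weights are preferable to inverse-variance weights by site. The simulated one-sided size of about 5.1% to 5.6% should be acknowledged. Age group and cataract severity are also absent from the safety test. Adding them would thin the strata further, so the SAP should say why they are left out.
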